4 STUDY POPULATIONS

4.1 Physician population

In total, 150 internists and rheumatologists practicing in hospitals or private clinics in Metropolitan France are expected to participate actively in the study (i.e. inclusion of at least 1 patient) (see also Section 3.4 for the physician recruitment method).

In order to avoid any over-representation of a particular site or hospital, a maximum of 10 patients per hospital department will be able to participate in the study. Each physician will have a specific site number.

4.2 Patient population

A total of 300 patients meeting the selection criteria listed below will be included in the study.

4.2.1 *Inclusion criteria*

Patients must meet the following criteria to be included in the study:

- » At least 50 years old.
- » Suffering from GCA as per investigator judgement, newly diagnosed or not.
- » Starting or under treatment for GCA.

- » Informed verbally and in writing about this study and not objecting to their data being electronically processed or subjected to data quality control.

4.2.2 *Non-inclusion criteria*

Patients fulfilling the following criteria cannot be included in the study:

- » Unable to consent
- » Participation to a randomised controlled clinical trial

4.2.3 *Withdrawal from the study*

In this cross-sectional study, no specific criteria are defined for withdrawal from the study. The patient can refuse at any time that his/her data are analysed.

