The index date was defined as the date of first occurrence of GCA code and cases were considered being incident if the GCA code first occurred after a minimal follow-up of 2 years. A treatment sequence was defined as the start of a new drug or the resumption of the same drug after a stop of drug dispensing ≥ 3 months. Annual incidence rates were calculated for the period 2009 to 2015 by using the people recorded in the EGB database as denominator.

Briefly, the results were the following: among the 752,717 patients recorded in the EGB database, 241 people fulfilled inclusion criteria with a mean follow-up of 3.7 (± 2.6) years. Annual incidence was ranging between 7 and 10/100,000 people ≥ 50 years-old that is 2300 patients/year. Demographic analyses showed that 72% of the patients were females and that mean age was 77.5 (± 8.9) years. 74.3% of the patients had at least one proxy (i.e ICD-10 code or a treatment) for hypertension, 39.4% for depression/insomnia and 33.6% for osteoporosis. After index date, temporal artery biopsy (TAB) was performed in 43.2%, high-resolution color Doppler ultrasound in 35.3% and 18FDG-positron emission tomography (PET) in 11.6%.

Regarding treatments, 84.3% of the patients used only GCs while 16.7% also received 1 to 3 adjunctive medications, mainly MTX. Mean 1st GCs sequence duration was 17.2 months (± 16.5) in 96.6% of the patients.

EGB database strengths included comprehensive patient demography, epidemiology, diagnostic methods and treatment sequences. In contrast, limited data were available for comorbidities (as only proxies were described), clinical presentations (cranial, polymyalgia rheumatica [PMR], extracranial), clinical forms (relapsing, GCs-dependant), doses of GCs used, cumulative GCs doses and GCs associated toxicities. In addition, patient journey was poorly described given that patients may be first seen by a variety of physicians according to their first signs and symptoms (e.g. ophthalmologist for blurred vision, neurologist for headache, etc.), data which was not available in the EGB database analysis.

The proportions of use of TAB, Ultrasound or PET have also to be confirmed as they thought to be unusually performed in the EGB analysis.

We propose to conduct an observational study aiming to describe GCA management and patient characteristics in France.

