2 STUDY OBJECTIVES

2.1 Primary objective

The primary objective is to describe medical practices in patients with GCA in terms of patient journey, diagnostic methods and specific GCA treatments since diagnosis.

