During this telephone contact or video, all the key points necessary to the proper conduct of the study will be addressed: the rationale and objectives of the study, regulatory requirements (patient information form, etc.), and also the technical requirements (data collection, shipment of the questionnaires, etc.). If the study is initiated by a telephone call, the minutes of the discussion and a presentation will be sent to the physician. In case of a study initiation by video, a quiz will be submitted to the physician to ensure that the training has been understood.

3.5 *Patient selection*

3.5.1 *Patient selection method*

Physicians will start patient inclusion only when the study is initiated at their site and when all regulatory authorisations are obtained.

It is expected that 300 patients (prevalent or incident cases) will be recruited in this study. Based on the previous EGB database analysis, there are 2300 incident patients/year in France. Thus, including 300 incident and prevalent patients during the recruitment period, even excluding summer holidays, seems realistic (see also Section 7.1).

Each physician will be requested to include consecutively during the inclusion period all the patients meeting the eligibility criteria listed below and accepting to participate in the study.

3.5.2 *Information and consent*

The physician must inform the patient about the study before inclusion and seek her/his non-opposition. A patient information form will be given to each patient by the physician. It will explain the purpose of collecting and processing the data, the nature of data collected, the persons who will receive the data, the patient's right to access and correct the data and also the patient's right to object to transmission of the data (as specified by the CNIL). The original will be kept by the investigator and a copy will be given to the patient.

Patients who are eligible to take part in the study and who verbally agree to their data undergoing automated processing (as defined by CNIL), will be included in the study by the physicians, who will enter the corresponding data in the eCRF. The patient agreement will be only verbal and will NOT include the collection of a non-opposition form.

Patient decision to participate or not in the study will be written in his/her medical file by the physician.

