9 LIMITATIONS OF THE STUDY

In order to extrapolate study results to the entire population, potential bias must be detected a priori and controlled as much as possible.

In this cross-sectional study, the description of patient management can be subject to selection bias during the recruitment of the study population (if the source population is not representative of the target population; if the active physician and included patient samples are not representative of the source population) (see also Section 7.1).

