- Proportion of patients with at least one general sign at diagnosis and the proportion of each sign (fever $>$ 38°C with no other etiology than GCA, weight loss and its value (%), alteration of the general condition)

For the value of ESR and CRP at diagnosis, only value measured in the previous month, the current month and the month following the date of diagnosis will be considered. For values at inclusion, only measures done within 6 month before the date of inclusion will be considered.

A listing of other initial characteristics related to GCA at diagnosis will be presented.

- Clinical form:
 - Proportion of patients with at least one relapse
 - In patient with at least one relapse:
 - Number of relapses per patient
 - Time between first relapse and diagnosis (months) ([APPENDIX](#))
 - Mean time between 2 consecutive relapses (months) ([APPENDIX](#))
 - The following information will be summarized by relapse:
 - Proportion of used criteria to assess relapse (Clinical/ Biological/ Imagery/ Other)
 - Proportion of patients using GCs just before the relapse
 - GCs dose at relapse diagnosis (mg/day)
 - Proportion of relapses of patients with Immunosuppressants just before the relapse
 - Proportion of relapses of patients with Targeted biologic therapy just before the relapse
 - Proportion of relapses of patients using other treatments just before the relapse
 - Proportion of relapses for which Glucocorticoids (GCs) were used as medical care for the relapse
 - GCs dose used for relapse medical care (mg/day)
 - Proportion of relapses for which Immunosuppressants were used as medical care for the relapse
 - Proportion of relapses for which Targeted biologic were used as medical care for relapse
 - Proportion of relapses for which other GCA (HORTON) treatments were used as medical care for relapse.
 - Distribution of GCs dependence
 - Current dose at inclusion (mg/day)
 - Number of kinetics per patient since diagnosis
 - Time between first kinetic and diagnosis (months) ([APPENDIX](#))
 - Proportion of patients with at least one kinetic ongoing at inclusion
 - Mean time between 2 consecutive kinetics (months) ([APPENDIX](#))
 - Total cumulative GCs dose according to investigator (excluding IV bolus) since diagnosis (mg) ([APPENDIX](#))
 - The following information will be summarized by Kinetic:
 - Kinetic duration (months) ([APPENDIX](#))
 - Proportion of kinetics with IV initial administration (bolus) (Yes/No)
 - If yes, total number of days

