9 TABLES AND LISTINGS

9.1 Disposition of patients

Keys information of the study:

- Date of inclusion of the first patient: DD/MM/YYYY
- Date of inclusion of the last patient: DD/MM/YYYY
- Enrollment duration (months): XX months
- Number of participating physicians: XX

[figure not shown]

Figure 2: Disposition of subjects

Table 1 - Subject Disposition - Study populations – Enrolled subjects (N=XX)

Parameter	Statistics	Total (N=XX)
Enrolled population No Yes	n (%) n (%) Filled, n(%) Missing, n(%)	
Analysis population No Yes	n (%) n (%) Filled, n(%) Missing, n(%)	
Reasons for non-inclusion from analysis population Reason 1: Age < 50 years old Reason 2: Not suffering from GCA per investigator judgement Reason 3: Not informed verbally and in written about the study or objecting to their data being electronically processed or subjected to data quality control Reason 4: Unable to consent Reason 5: Participation to a randomized controlled clinical trial Reason 6 : Not starting or not under treatment for GCA	n (%) n (%) n (%) n (%) n (%) n (%) n (%)	

The percentages are calculated compared to filled data

STUDY : CHUGAI-ARTEMIS - Edition date: DDMMYY

Pgm : DESCR\DISPO.SAS

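### Only patients starting or on treatment are eligible, yet results are worded for all patients with GCA and pooled over very different times since diagnosis

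*Protocol*

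**What the plan says.** Protocol 4.2.1, repeated in SAP 3.5.1.1, requires patients to be "Starting or under treatment for GCA". SAP Table 1 enforces this: "Not starting or not under treatment for GCA" is a listed reason for leaving the Analysis Population. Data come from one visit, and Protocol 3.5.1 mixes newly diagnosed and established cases: "It is expected that 300 patients (prevalent or incident cases) will be recruited in this study".

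The objective has no such restriction. Protocol 2.1 reads "The primary objective is to describe medical practices in patients with GCA" and covers treatments since diagnosis. Protocol 9 opens with "In order to extrapolate study results to the entire population, potential bias must be detected a priori and controlled as much as possible". It then names two routes to selection bias: a source population unlike the target, and "if the active physician and included patient samples are not representative of the source population". The controls in 9.1 are the physician source list, consecutive inclusion, a comparison of active physicians with that list, and a comparison of patient characteristics with the literature. None of these passages mentions patients who have come off treatment.

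Breakdowns in the analysis plan:

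- **Clinical form** (relapse, GC courses, cumulative dose, complications; SAP 5.5.2): overall, by incident or prevalent status (6-week threshold), by diagnostic delay and by following physician.
- **Specific GCA treatments**, part of the primary objective (Protocol 7.2.3.1, SAP 5.4): overall and by physician type.
- **GC-related comorbidities** (SAP 5.5.1): overall and by physician type.
- **Time from diagnosis to inclusion**: derived in SAP Appendix (3) and summarised in Table 14, but not used to break down any other table beyond the 6-week split.

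**The concern.** A patient who was treated, stopped and stayed well is structurally absent, however faithfully sites recruit consecutively. A patient treated for three years can be caught at a visit over a period about three times as long as one treated for a year. The prevalent sample therefore leans towards long courses.

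Relapse, number of GC courses, cumulative dose, GC-related comorbidity and use of adjunct drugs all plausibly depend on course length and on time since diagnosis. Reported as features of GCA in France, they would be attributed to a population that was not sampled. The literature comparison in Protocol 9.1.2 could then show differences created by eligibility. The sponsor's earlier EGB claims-database study (Protocol 1) selected on GCA codes and GC dispensings around an index date, not on being under treatment at a later visit.

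**Working it through.** The plan states no derived figure to reproduce; Protocol 7.1.1 calls sample size not applicable. The check asks how strongly the criterion tilts the sample.

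**Input.** Protocol 1: "Mean 1st GCs sequence duration was 17.2 months (± 16.5) in 96.6% of the patients". So μ = 17.2 and σ = 16.5 months.

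**Assumptions.** Incidence is steady, the first GC sequence stands in for the treated course, and the chance of a visit in the window does not depend on course length.

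**Mean full course at one moment.** Each course D is sampled in proportion to its length:

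E[D²]/E[D] = μ + σ²/μ = 17.2 + 272.25/17.2 = 33.0 months, and 33.0/17.2 = 1.92.

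**Allowing for a recruitment window of W months.** The weight becomes D + W, so the mean is (E[D²] + Wμ)/(μ + W), with E[D²] = 295.84 + 272.25 = 568.09.

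| W | Source | Mean full course | Ratio to 17.2 |
|---|---|---|---|
| 0 | single moment | 33.0 | 1.92 |
| 3 | SAP 3.3 | (568.09 + 51.6)/20.2 = 30.7 | 1.78 |
| 5 | Protocol 3.3 | (568.09 + 86.0)/22.2 = 29.5 | 1.71 |

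The 4-month duration in Protocol 11 falls between the last two rows.

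**Share of long courses.** Gamma and lognormal shapes were matched to the same mean and SD (the shapes are assumed). Courses over 24 months make up 21% (lognormal) to 25% (gamma) of all courses. They make up 50% to 58% of courses caught at one moment, and 43% to 50% with a 5-month window.

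**What is recorded at the visit.** The full course includes time after inclusion. On average half has elapsed at a single moment: 33.0/2 = 16.5 months, slightly below the unselected mean of 17.2. Relapses, GC courses and cumulative dose are counted only over this elapsed part.

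**Spread of time since diagnosis.** With S(t) the proportion of courses longer than t, the share of a single-moment sample between times a and b is the integral of S from a to b, divided by μ. Treatment is taken to start at diagnosis:

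| Time since diagnosis | Share (range over the two shapes) | Of 300 |
|---|---|---|
| ≤6 weeks | about 8% | about 24 |
| >6 weeks to 12 months | 43% to 48% | 130 to 143 |
| >12 to 24 months | 23% to 25% | 70 to 76 |
| >24 months | 21% to 23% | 62 to 70 |

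The 6-week split thus separates a small group with almost no time to relapse from a prevalent group running from 6 weeks to several years.

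**The case against.** **The limitations section already covers this.** Protocol 9 does raise source versus target population, so it would be wrong to say that it considers only physicians and included patients. It also does not define the entire population as everyone ever diagnosed. That stands, but the specific exclusion remains unnamed and the objective remains unrestricted.

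**Much of the primary objective is untouched.** Patient journey and diagnostic methods concern events around diagnosis. Most of the affected outputs are secondary; the exception is treatment since diagnosis. This stands and limits the reach of the point.

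**The study is not biased for treated patients.** For patients currently under treatment, this selection is no error. That also stands, and is why the remedy is to narrow the claim and leave eligibility alone.

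**The size is model-based.** More frequent visits early in treatment would lower the ratio, and the first sequence may understate total treated time. Both are fair.

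Two stronger readings are tempting, and the documents support neither:

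- A reader might infer that relapse and cumulative dose will be overestimated. The 1.7 to 1.9 ratio concerns full courses, whereas these endpoints stop at the visit. Over-representation of long courses and truncation at inclusion can pull in opposite directions, and the documents give no relapse timing from which to find the balance.
- A reader might infer that the Table 18 row "Proportion of patients with at least one kinetic ongoing at inclusion" is an uninformative rate of GC dependence. The SAP lists it as one of several descriptors and never calls it such a rate. Its negative category identifies treated patients who are off GCs, which is useful information.

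**Conclusion.** The point holds as a mismatch between the population sampled and the population described. It merits a change because the change is cheap and affects what the study may conclude. Under steady incidence, with the first GC sequence as proxy and visits unrelated to course length, sampled patients have full courses averaging 29 to 33 months against 17.2 unselected. The excess of long courses follows from the design; its exact size rests on those assumptions.

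The direction of error in pooled relapse, GC-course and cumulative-dose figures is undetermined. What can be said is that these figures mix very different times since diagnosis. Clinical form has only a 6-week split on that scale, and the primary treatment tables and GC-related comorbidities have none.

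**What to change.** Leave the eligibility criterion as it is.

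1. In Protocol 2 and 9 and in the study report, define the target population as patients starting or under treatment for GCA. State in Protocol 9 that patients who have stopped treatment are excluded and that long courses are therefore over-represented. Drop extrapolation to all GCA patients.
2. Present SAP Tables 6-12 and 16-20 also by time since diagnosis, using the interval in SAP Appendix (3). Possible bands are ≤6 weeks, >6 weeks to 12 months, >12 to 24 months, and >24 months.
3. In the Protocol 9.1.2 literature comparison, set these patients against patients on treatment at a similar time since diagnosis, or state that the comparison is not like with like.

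No new data, visits or patients are needed. The cost is a narrower claim, extra table columns and smaller cells. The first band is the thinnest, at about 24 of 300 in a single-moment sample; a recruitment window with prompt visits by new patients would raise that. If a band proves too small, merge it with its neighbour and say so.

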5 CONDUCT OF THE STUDY AND DATA TO BE COLLECTED

5.1 Conduct of the study

5.1.1 *Inclusion consultation (single study visit)*

Once the study initiation has been completed, patients will be included consecutively after verification that they meet the selection criteria (see section 4.2).

The information will be collected during a single visit to the internists and rheumatologist as part of the usual patient management of his/her GCA. The physician will explain the purpose of the study to the patient with an information form specific to the study and will inform him/her of the option to refuse or withdraw from participation. A copy of the information form will be given to the patient and the original will be kept by the physician.

The physician will perform this visit as part of the usual patient management and will not perform any additional examinations specific to the study.

The data collected from the medical file will be recorded on an electronic case report form (eCRF). Self-assessment questionnaires about health status (SF-36, EQ-5D), GCA activity (global arteritis activity VAS) and fatigue (FACIT-fatigue) (see also Section 5.3.2) will be proposed to the patient. He/she will have to complete them during the course of the visit. The physician will also complete a copy of the global arteritis activity VAS on paper. All questionnaires will be returned in the pre-paid reply envelope to the CRO ITEC Services, in charge of the data entry.

5.2 Physician Data collected

The following data will be collected from the physicians who have agreed to participate:

- » Physician location

- » Gender
- » Medical specialty
- » Type of activity: public hospital, private hospital, both hospital and office-based, other
- » Number of GCA diagnosis within the last previous year
- » Year of medical school graduation
- » Number of years of practice

The analyses of this data will allow to identify any physician recruitment bias (see also Section 9.1.2).

The information will be recorded by the physician in the eCRF.

5.3 Patient Data collected

Patient identity will be coded in the eCRF and the self-assessment questionnaires. Patients will be identified using a number made up of 4 digits: 3 digits for the investigator and 1 digits for the inclusion order number (see also Section 12.5 on data confidentiality).

5.3.1 Case report form

No information related to patient identity (initials, full date of birth, etc) will be entered in the eCRF.

The following information will be recorded in the eCRF using the data available in the medical file or collected during the visit (as part of the routine patient management):

- » Date of the inclusion visit (the only study visit) and type of visit (outpatient visit, day hospital, in-patient hospitalisation).
- » Patient eligibility criteria.
- » Demographic data:
 - Year of birth, gender,
 - Smoking status (smoker, never smoker),
- » Clinical data:
 - Height, weight (at diagnosis, at the inclusion visit)
 - Medical history:
 - significant past and current comorbidities (e.g. diabetes, high blood pressure, dyslipidaemia, osteoporosis, neuropsychiatric disorders,

depression, insomnia, serious infection disease, parasitic diseases, cancer, stroke, coronary artery disease, ischemic cardiopathy, peripheral artery diseases, adrenal insufficiency, cataract, glaucoma, gastro-intestinal ulcer, digestive perforation, other significant history),

- start and stop date (month, year) of comorbidities
- Comorbidities related to GCs for GCA patients (i.e. which appeared or worsened during GCs treatment according to the investigator judgement).

» GCA patient journey:

- Incident or prevalent patient:
 - Newly diagnosed (i.e. incident) patient will be defined as patient with GCA diagnosis within the last 6 weeks before visit
 - Not newly diagnosed (i.e. prevalent) patients will be defined as patient with GCA diagnosis more than 6 weeks before visit
- Date of initial diagnosis
- Date of GCA signs/symptoms (month and year)
- Physician(s) who referred the patient (General Practitioner, Ophthalmologists, Neurologist, Emergency, Internist, Rheumatologist, Other).

» GCA characteristics:

- Initial presentation at diagnosis and inclusion visit:
 - Cranial (localized headache, scalp tenderness, temporal artery tenderness or decreased pulsation, ischemia-related vision impairment / loss, mouth or jaw pain upon mastication, stroke or transient ischaemic attack (TIA), other)
 - PMR (morning stiffness and/or pain in the shoulder and/or pelvic girdles, inflammatory arthromyalgia, peripheral arthritis, other)
 - Extracranial (large-vessel GCA i.e. thoracic or abdominal aortic aneurysm, myocardial infarction, dilatation, limb claudication, subclavian stenosis, other)
 - ESR/CRP
 - General signs: fever, weight loss (%), health status modification

Start date for all signs and symptoms (month, year)

- Diagnostic methods: TAB, High-resolution color Doppler ultrasound of the temporal arteries, MRI of the temporal arteries, 18FDG-PET, Computed tomography

angiography (CTA), Magnetic resonance angiography, signs/symptoms, erythrocyte Sedimentation Rate (ESR), C-Reactive protein (CRP), other.

○ Clinical form:

- Relapses: date (month, year), treatments and doses, criteria for identifying relapse (clinical, biological, other)
- GCs-dependence: dose of prednisone after GCA diagnosis
- Complications during the course of the disease: ischemia-related vision loss, stroke, TIA, thoracic or abdominal aortic aneurysm, other.

» GCA activity:

- Clinical signs and symptoms of GCA activity at diagnosis and at inclusion: GCA-related fever ($> 38^{\circ}\text{C}$), symptoms of PMR (morning stiffness and/or pain in the shoulder and/or pelvic girdles, inflammatory arthromyalgia, peripheral arthritis, other), localised headache, temporal artery or scalp tenderness, visual signs or symptoms (e.g. acute or subacute vision loss due to arteritic anterior ischemic optic neuropathy; A-AION), transient blurry vision (generally monocular or at least affecting one eye at a time, but potentially affecting both eyes), jaw or mouth pain, extremity claudication, other features judged by the investigator to be consistent with a GCA or PMR flare.

Start date of signs and symptoms (month, year)

» Treatments:

- Previous and on-going specific GCA treatments since diagnosis:
- GCs (start and end date, dose/day, administration route, current dose, cumulative dose, kinetic)
 - Immunosuppressants (MTX, cyclophosphamide, cyclosporine, azathioprine, mycophenolate mofetil, leflunomide, dapsone, hydroxychloroquine, other) (start and end date, dose at starting date, current dose, maximum dose)
 - Targeted biologic therapy (adalimumab, etanercept, abatacept, tocilizumab, infliximab, other) (start and end date, dose at starting date, current dose)
 - Janus Kinase inhibitors (start and end date, dose at starting date, current dose)
- Treatments at diagnosis and inclusion visit: antiplatelet agents, statins, antiosteoporotic treatments, antihypertensive (start date, treatment name).
- Other significant concomitant treatments (start and end date, indication)

- Treatments for comorbidities related to GC intake (start and end date, indication)

No safety data will be collected. Physicians will report adverse event as per usual French process, if appropriate.

5.3.2 **Questionnaires**

Four paper questionnaires will be completed by the patient and one will be completed by the physician. All questionnaires will be returned in the pre-paid reply envelope to the CRO ITEC Services, in charge of the data entry.

5.3.2.1 *Self-assessment patient questionnaires:*

- ▷ SF-36 (McHorney, Ware, et Raczek 1993; Ware et Sherbourne 1992): The SF-36 questionnaire is a generic health status instrument evaluating 8 dimensions through 36 questions: physical functioning, bodily pain, role limitations due to physical health problems, role limitations due to personal or emotional problems, emotional well-being, social functioning, energy/fatigue, and general health perceptions. An additional item provides an indication of perceived change in health (Annexe 15.1).
- ▷ EQ5D-3L (Brooks 1996; EuroQol Group 1990; Rabin et al. 2014): The EQ-5D questionnaire is a generic health status instrument composed of 5 questions and a VAS. The questions explore 5 dimensions: mobility, self-care, usual activities, pain/discomfort and anxiety/depression. Each dimension has 3 levels: no problems, some problems, extreme problems. The visual analogue scale evaluates the perceived health state (Annexe 15.2).
- ▷ FACIT-fatigue (Webster, Cellier, et Yost 2003): FACIT-Fatigue is an instrument that measures overall fatigue and its effects on the general functioning and daily activities through 13 questions. Completion of the questionnaire should be based on a 7-day recall period. Each question has 5 levels: not at all, a little bit, somewhat, quite a bit, very much. Lower scores indicate greater fatigue (Annexe 15.3).
- ▷ Patient global arteritis activity VAS: This VAS measures global arteritis activity on a scale of 100 mm labelled with “no disease activity” (symptom-free and no arteritis symptoms) at the extreme left and with “maximum disease activity” (maximum arteritis disease activity) at the extreme right. The patient will be asked to indicate his/her disease activity by drawing a line on the scale (Annexe 15.4).

5.3.2.2 *Physician questionnaire:*

- ▷ Physician global arteritis activity VAS: This VAS measures global arteritis activity, as described above. The physician will be asked to indicate the patient disease activity by drawing a line on the scale.

